5.1.3 Statistical Methods for Observational Objective(s)

Immunogenicity

All analyses will be descriptive; no hypotheses will be tested.

For GMTs and GMCs, 95% CIs of point estimates will be calculated using the normal approximation assuming antibody titers/concentrations are log normally distributed. For proportions, 95% CIs of point estimates will be calculated assuming proportions follow a binomial distribution using the Exact method.

Descriptive analyses on A, C, W, and Y serogroups will include:

- hSBA and rSBA GMTs and corresponding 95% CIs
- hSBA and rSBA titer distribution and RCDCs
- Percentages of subjects with hSBA titer $\geq 1:4$ and $\geq 1:8$ and corresponding 95% CIs
- Percentages of subjects with rSBA titer $\geq 1:8$ and $\geq 1:128$ and corresponding 95% CIs
- Proportion with at least a 4-fold increase in hSBA and rSBA antibody titer compared to baseline (Group 1 and Group 2 during Stage I and Group 3 and Group 4 during Stage II)
 - An hSBA vaccine seroresponse for serogroups A, C, W, and Y is defined as a post-vaccination titer $\geq 1:16$ for subjects with pre-vaccination titer $< 1:8$, or a post-vaccination titer ≥ 4 times the pre-vaccination titer for subjects with a pre-vaccination titer $\geq 1:8$.
 - An rSBA vaccine seroresponse is defined as a post-vaccination titer $\geq 1:32$ for subjects with pre-vaccination rSBA titer $< 1:8$, or a post-vaccination titer ≥ 4 times the pre-vaccination titer for subjects with pre-vaccination rSBA titer $\geq 1:8$.
- Ratio of the GMT post-vaccination/GMT pre-vaccination and the associated 95% CI of the ratio (at Day 30 for Group 1 and Group 2 and at Day 6 in the subset of Group 1 and Group 2 [during Stage I], and at Day 30 for Group 3 and Group 4 [during Stage II]).

Descriptive analyses on anti-tetanus antibody concentrations will include:

- Geometric mean concentrations (GMCs) at Day 0 (all groups), 2 years after enrollment (Groups 3 and 4), and 30 (window, + 14) days after the administration of a single dose of MenACYW conjugate vaccine in Study MEQ00066 (Groups 1–4)
- Proportion of subjects achieving seroprotective antibody levels ≥ 0.01 IU (international units) /mL, ≥ 0.1 IU/mL, and ≥ 1.0 IU/mL to tetanus toxoid 30 (window, + 14) days after the administration of a single dose of MenACYW conjugate vaccine in Study MEQ00066 (Groups 1–4)
- RCDCs and kinetic curves

Safety

All analyses will be descriptive; no hypotheses will be tested.

Safety results will be described for subjects revaccinated with MenACYW conjugate vaccine (i.e., Groups 1–4). The main parameters for the safety endpoints will be described by 95% CIs (based on the Clopper-Pearson method).

The frequency and percentage of subjects who had solicited injection site and systemic reactions and their 95% CIs will be provided. These events will be tabulated by type of reactions and intensity for each study group. These events will also be summarized by other categories specified in the endpoints (e.g., time of onset, number of days of occurrence, action taken).

Unsolicited AEs will be collected, coded, and summarized by MedDRA system organ class and PT. For each unsolicited AE, the number of subjects with at least one instance of that event will be reported. Unsolicited AEs will also be tabulated by intensity and relatedness of study vaccine and by other categories specified in the endpoints.

Immediate reactions, SAEs, and any event that leads to subject withdrawal from the study will be tabulated separately.

Table 5.2: Statistical Analyses for Safety Observational Objective at Stage I (Groups 1 and 2) and Stage II (Groups 3 and 4)

Safety Events	Time and Group	Description
Immediate unsolicited non-serious systemic AE	Within 30 minutes after vaccination for all subjects in Groups 1 – 4	Percentage of subjects that have the event, MedDRA terms, intensity, relationship to vaccine, study discontinuation
Solicited injection site reactions	Within 7 days after vaccination for all subjects in Groups 1 – 4	Percentage of subjects that have the event, onset, duration, intensity, action taken, study discontinuation, temperature collection routes
Solicited systemic reactions	Within 7 days after vaccination for all subjects in Groups 1 – 4	Percentage of subjects that have the event, MedDRA terms, onset, duration, intensity, relationship, action taken, study discontinuation
Unsolicited non-serious AEs/ARs	Within 30 days after vaccination for all subjects in Groups 1 – 4	Percentage of subjects that have the event, MedDRA terms, onset, duration, intensity, relationship, action taken, study discontinuation
AEs leading to study discontinuation	Within 30 days after vaccination for all subjects in Groups 1 – 4	Percentage of subjects that have the event, MedDRA terms, time of onset, duration, intensity, relationship, action taken, study discontinuation
SAEs (including AESIs)	Within 7 days after vaccination for all subjects in Groups 1 – 4 Within 30 days after vaccination for all subjects in Groups 1 – 4	Percentage of subjects that have the event, MedDRA terms, onset, duration, relationship, seriousness criteria, outcome, study discontinuation
MAAEs	Within 30 days after vaccination for all subjects in Groups 1 – 4	Percentage of subjects that have the event, MedDRA terms, onset, duration, relationship, seriousness criteria, outcome, study discontinuation

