Medical and scientific judgment should be exercised in deciding whether expedited reporting is appropriate in other situations, such as IMEs that may not be immediately life-threatening or result in death or hospitalization but may jeopardize the health of the subject or may require intervention to prevent one of the other outcomes listed in the definition above. These IMEs should also usually be considered serious. Examples of such events include allergic bronchospasm requiring intensive treatment in an emergency room or at home, blood dyscrasias or convulsions that do not result in inpatient hospitalization, or the development of drug dependency or drug abuse, new-onset diabetes, or autoimmune disease.

Adverse Reaction:

All noxious and unintended responses to a medicinal product related to any dose should be considered adverse reactions (AR).

(The phrase “responses to a medicinal product” means that a causal relationship between a medicinal product and an AE is at least a reasonable possibility)

^a The term “life-threatening” refers to an event in which the subject was at risk of death at the time of the event; it does not refer to an event which hypothetically might have caused death if it were more severe.

^b All medical events leading to hospitalizations will be recorded and reported as SAEs, with the exception of: hospitalization planned before inclusion into the study or outpatient treatment with no hospitalization.

^c “Persistent or significant disability or incapacity” means that there is a substantial disruption of a person’s ability to carry out normal life functions.

The following additional definitions are used by Sanofi Pasteur:

Immediate Event/Reaction:

Immediate events are recorded to capture medically relevant unsolicited systemic AEs (including those related to the product administered) that occur within the first 30 minutes after vaccination.

Solicited Reaction:

A solicited reaction is an “expected” AR (sign or symptom) observed and reported under the conditions (nature and onset) prelisted in the protocol and CRB (e.g., injection site pain or headache occurring between Day 0 and Day 7 post-vaccination). By definition, solicited reactions are to be considered as being related to the product administered.

For injectable vaccines, solicited reactions can either be solicited injection site reactions or solicited systemic reactions.

Unsolicited AE/AR:

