An unsolicited AE is an observed AE that does not fulfill the conditions prelisted in the CRB in terms of diagnosis and/or onset window post-vaccination. For example, if headache between Day 0 and Day 7 is a solicited reaction (i.e., prelisted in the protocol and CRB), then a headache starting on Day 7 is a solicited reaction, whereas headache starting on Day 8 post-vaccination is an unsolicited AE. Unsolicited AEs include both SAEs and non-serious unsolicited AEs.

Medically Attended AE (MAAE)

An MAAE is a new onset or a worsening of a condition that prompts the subject to seek unplanned medical advice at a physician’s office or emergency department. A physician contact made over the phone or by email will be considered a physician office visit for the purpose of MAAE collection. This definition excludes pre-planned medical office visits for routine medical care, as well as follow-up visits of chronic conditions with an onset prior to entry in the study. An AE discovered during a planned routine visit (e.g., upper respiratory tract infection, otitis) will be collected as an MAAE.

Injection Site Reaction:

An injection site reaction is an AR at and around the injection site. Injection site reactions are commonly inflammatory reactions. They are considered to be related to the product administered.

Systemic AE:

Systemic AEs are all AEs that are not injection or administration site reactions. They therefore include systemic manifestations such as headache, fever, as well as localized or topical manifestations that are not associated with the vaccination or administration site (e.g., erythema that is localized but that does not occur at the injection site).

Adverse Event of Special Interest (AESI):

An AESI is an event for which ongoing monitoring and rapid communication by the Investigator to the Sponsor must be done. Such an event might warrant further investigation in order to characterize and understand it. Depending on the nature of the event, rapid communication by the study Sponsor to other parties (e.g., regulators) might also be warranted.

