4.3.2.2 Safety Endpoints

The observational endpoints for the evaluation of safety are:

- Occurrence, nature (Medical Dictionary for Regulatory Activities [MedDRA] preferred term), duration, intensity, and relationship to vaccination of any unsolicited systemic AEs reported in the 30 minutes after vaccination.
- Occurrence, time to onset, number of days of occurrence, intensity, action taken, and whether the reaction led to early termination from the study, of solicited (prelisted in the subject's diary card and CRB) injection site reactions occurring from Day 0 through Day 7 after vaccination.
- Occurrence, time to onset, number of days of occurrence, intensity, action taken, and whether the reaction led to early termination from the study, of solicited (prelisted in the subject's diary card and CRB) systemic reactions occurring from Day 0 through Day 7 after vaccination.
- Occurrence, nature (MedDRA preferred term), time to onset, duration, intensity, action taken, relationship to vaccination (for systemic AEs only), and whether the event led to early termination from the study, of unsolicited AEs occurring from Day 0 through ~Day 30 after vaccination. MAAEs will be collected as unsolicited non-serious AEs from Day 0 through ~Day 30 after vaccination.
- Occurrence, nature (MedDRA preferred term), time to onset, duration, seriousness criteria, relationship to vaccination, outcome, and whether the event led to early termination from the study, of SAEs, including AESIs, throughout the study.

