4.4.2.3.2 Time of Onset

Time of onset will be computed using the same methodology as for unsolicited non-serious AEs described in [Section 4.4.2.2.4](#).

SAEs will be analyzed throughout the study using the following periods:

- Within 30 days
- During the study (i.e., all SAEs that occurred during the study)

An SAE with missing time of onset will be considered to have occurred just after the vaccination indicated by the visit number, so will be included in these tables.

Note: SAEs that occurred before vaccination (negative time of onset) will not be included in analysis, but will be listed separately.

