5.3.1.1 Immediate

For unsolicited non-serious systemic AEs, a missing response to the “Immediate” field is assumed to have occurred after the 30-minute surveillance period and will not be imputed.

For SAEs, missing or partially missing elapsed time from last vaccination recorded if within 24 hours will remain missing and not be imputed. Such SAEs will not be considered as immediate.

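### Table 5.2 limits the 30-minute analysis to non-serious events, although the immediate-AE endpoint is not so limited and the SAP foresees immediate SAEs

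*SAP*

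**What the plan says.** **Endpoint and definitions.** SAP 4.3.2.2 lists as its first safety endpoint the occurrence, nature, duration, intensity and "relationship to vaccination of any unsolicited systemic AEs reported in the 30 minutes after vaccination". It sets no limit on seriousness. The definition in 4.3.2.1 sets none either: "Immediate events are recorded to capture medically relevant unsolicited systemic AEs (including those related to the product administered"), within 30 minutes of vaccination. The same section fixes the scope of the term: "Unsolicited AEs include both SAEs and non-serious unsolicited AEs".

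**Planned analysis.** Section 5.1.3 says "Immediate reactions, SAEs, and any event that leads to subject withdrawal from the study will be tabulated separately". Table 5.2, in that section, has a single 30-minute row, labelled "Immediate unsolicited non-serious systemic AE". Its SAE row gives two windows: "Within 7 days after vaccination for all subjects in Groups 1 – 4 Within 30 days after vaccination for all subjects in Groups 1 – 4". Section 4.4.2.3.2 says "SAEs will be analyzed throughout the study using the following periods" and then names 30 days and the whole study.

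**Missing-data rule.** Section 5.3.1.1 deals with SAEs whose elapsed time from vaccination, recorded when it is within 24 hours, is missing or incomplete: "Such SAEs will not be considered as immediate".

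**The concern.** The immediate endpoint is there to describe acute systemic events after vaccination. Under the endpoint and definitions, a serious systemic event ten minutes after the injection is an immediate event. Under the row label in Table 5.2 it is not counted in the 30-minute percentage. A programmer who follows Table 5.2 and a reader who follows 4.3.2.2 would therefore expect different numerators for the same quantity. The two differ only when a serious immediate event occurs, and the immediate table could then show zero. What is at stake is whether one descriptive percentage matches its own endpoint, and whether a serious event at 30 minutes can be identified as such in the tables the SAP specifies.

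**Working it through.** The SAP states no figure on this point, so there is nothing to reproduce. The check is mainly a comparison of its sections, with a small illustration of size.

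**Step 1: compare scopes.**

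| Place in SAP | What it covers | Are SAEs in the first 30 minutes counted as immediate? |
|---|---|---|
| 4.3.2.1, immediate event | Unsolicited systemic AEs within 30 minutes | Yes; unsolicited AEs include SAEs |
| 4.3.2.2, first endpoint | Any unsolicited systemic AE within 30 minutes | Yes |
| 5.3.1.1 | SAEs with missing or incomplete elapsed time are not immediate | Implied yes when elapsed time is known |
| Table 5.2, immediate row | Non-serious systemic AEs within 30 minutes | No |
| Table 5.2, SAE row | SAEs within 7 and 30 days | Counted, but not as immediate |
| 4.4.2.3.2 | SAEs within 30 days and during the study | Counted, but not as immediate |

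The first three rows disagree with the fourth, and the last two do not fill the gap.

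**Step 2: can SAE onset recover the endpoint?** Section 4.4.2.3.2 computes SAE onset as 4.4.2.2.4 does, as start date minus vaccination date. A serious event at 10 minutes and another 12 hours later on the same date both have onset Day 0. The tabulated onset cannot separate them.

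**Step 3: does the 5.3.1.1 rule have a use?** Excluding SAEs with unknown elapsed time from the immediate category matters only if SAEs with known elapsed time can fall in it. Table 5.2 and 4.4.2.3.2 name no analysis that uses the category for SAEs.

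**Step 4: illustration of size.** Inputs are the planned group sizes in 5.5 (180 in each of Groups 1 and 2, 40 in each of Groups 3 and 4) and the 95% Clopper-Pearson interval named in 5.1.3. The assumption, not taken from the SAP, is that exactly one subject in a group has an immediate event and that this event is serious. All planned subjects are taken as vaccinated.

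- For 0 of n: lower limit 0, upper limit 1 − 0.025^(1/n).
- For 1 of n: lower limit 1 − 0.975^(1/n); upper limit is the 0.975 quantile of a Beta(2, n − 1) distribution.

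| Group size | Table 5.2 as labelled | Endpoint as worded |
|---|---|---|
| 180 | 0/180 = 0% (0 to 2.0%) | 1/180 = 0.56% (0.01 to 3.06%) |
| 40 | 0/40 = 0% (0 to 8.8%) | 1/40 = 2.5% (0.06 to 13.2%) |

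**The case against.** The strongest reply is that separating non-serious AEs from SAEs is a deliberate and coherent scheme. Section 4.3.2.3.1 gives events in the observation period different routes: unsolicited systemic AEs are entered as immediate AEs, while SAEs are handled like any other SAE. In 4.3.2.2 SAEs have their own endpoint, with seriousness criteria and outcome, which the immediate endpoint lacks. Section 5.1.3 announces separate tabulations. This shows how the label in Table 5.2 may have arisen, but it does not remove the mismatch. For the 30-day period the non-serious row has an SAE counterpart; for 30 minutes it has none. The sentence on separate tabulation does not say where an event that is both immediate and serious belongs.

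A reader might infer that the plan drops the most serious acute reactions from the report. The SAP does not support that. Any such event falls inside both SAE windows of Table 5.2 and is shown there with relationship, seriousness criteria and outcome.

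A reader might also infer that no output at all will treat an SAE as immediate. That cannot be established. Table 5.2 is not a complete list of outputs, since 4.4.2.5.6 mentions a disposition table and a safety overview table that it does not contain, and the table shells are not in the document. What can be said is that neither Table 5.2 nor 4.4.2.3.2 names such an analysis.

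**Conclusion.** The inconsistency stands and is minor. The endpoint and definitions include serious immediate events, 5.3.1.1 foresees them, and the one 30-minute analysis specified in Table 5.2 excludes them. If the plan is followed as written, such an event would be missing from the immediate-event percentage and, in the SAE analyses, indistinguishable from other Day 0 SAEs.

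The size is hypothetical. The SAP gives no rate for serious events within 30 minutes, and the contrast in a group of 180 or 40 rests on assuming one affected subject with no other immediate event. If none occurs, the two versions agree. The figures are given by group because 5.1.3 specifies no pooled safety percentage across groups. All safety analyses are descriptive under 5.1.3, so no hypothesis test, immunogenicity estimate or sample size is affected.

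**What to change.** Relabel the row in Table 5.2 as *Immediate unsolicited systemic AEs (serious and non-serious)* and show the serious events as a sub-row. Classify an SAE as immediate from the elapsed time referred to in 5.3.1.1, and keep the existing rule that an SAE with missing or incomplete elapsed time is not immediate. Keep all these events in the SAE tables, and add a footnote that an event may appear in both places so that the counts are not summed.

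The cost is SAP wording, one sub-row in a table shell, and the same event shown in two tables. No new data should be needed, provided the recorded elapsed time is fine enough to identify 30 minutes; the SAP implies that it is collected but does not give its precision.

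The alternative is to restrict the endpoint in 4.3.2.2 to non-serious events and state that immediate SAEs appear only in the SAE tables. That also removes the contradiction, but it narrows the endpoint and leaves the SAE rule in 5.3.1.1 without a named use, so the relabelled row is preferable.

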5.2 Analysis Sets

5.2.1 Stage I Analysis Sets

5.2.1.1 Full Analysis Set

The Stage I Day 30 FAS (FAS1) is defined as subjects in Groups 1 and 2 who received the study vaccine and have a valid serology result for at least 1 serogroup from a BL provided 30 (window, +14) days post-vaccination.

The Stage I Day 6 FAS (FAS2) is defined as the subset of Group 1 and 2 subjects who received the study vaccine and have a valid serology result for at least 1 serogroup from a BL provided 6 (window, 5–7) days post-vaccination.

The Stage I FAS for persistence (FAS3) includes subjects in Groups 1, 2, 3, 4, 5 and 6 who have a valid serology result for at least 1 serogroup from a pre-vaccination BL (3-year or 6–7-year antibody persistence).

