5.2.1.2 Per-Protocol Analysis Sets

5.2.1.2.1 Day 30 Per-Protocol Analysis Set

Groups 1 and 2

The Stage I Day 30 Per-Protocol Analysis Set (PPAS1) is a subset of Stage I Day 30 FAS (FAS1). Subjects with at least 1 of the following relevant protocol deviations will be excluded from the PPAS1:

- Subject did not meet all protocol-specified inclusion criteria or met at least 1 of the protocol-specified exclusion criteria
- Subject did not receive MenACYW conjugate vaccine according to randomization
- Preparation and/or administration of vaccine was not done as per-protocol
- Subject did not receive vaccine in the proper time window
- Subject did not provide a post-dose serology sample in the pre-specified time window at 30 (window, + 14) days post-vaccination
- Subject received a protocol-prohibited therapy/medication/vaccine that might impact antibody response to the study vaccine
- Subjects received study vaccine deemed unacceptable for use (e.g., because of a temperature excursion).
- Subject's post-vaccination serology sample did not produce a valid test result for any antigen (i.e., results for all antigens are missing)
- Any other deviation identified during conduct of the study and judged by the clinical team during data review as having a potential impact on the assessment of immunogenicity

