5.2.2 Stage II Analysis Sets (Groups 3 and 4)

5.2.2.1 Full Analysis Sets

The Stage II Day 30 FAS (FAS4) is defined as subjects in Groups 3 and 4 who received the study vaccine and have a valid serology result for at least 1 serogroup from a BL provided 30 (window, +14) days post-vaccination.

The Stage II FAS for persistence (FAS5) includes subjects in Groups 3 and 4 who have a valid serology result for at least 1 serogroup from a pre-vaccination BL (5-year antibody persistence).

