5.2.3 Populations Used in Analyses

5.2.3.1 Stage I

The primary immunogenicity analyses will be performed on the Stage I Day 30 PPAS (PPAS1) and will be confirmed on the Stage I Day 30 FAS (FAS1). In the FAS1, subjects will be analyzed by the vaccine group to which they were randomized.

The secondary immunogenicity analyses (Day 6 subset) will be performed on the Day 6 PPAS (PPAS2) and Day 6 FAS (FAS2).

The secondary antibody persistence analyses will be performed on the FAS3.

The safety analysis will be performed on the Stage I Analysis Set (SafAS1). Subjects will be analyzed according to the vaccine they actually received.

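### FAS1 already carries the Day 30 sampling window, so the analysis named to confirm the primary result cannot show the effect of dropping off-window samples

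*SAP*

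**What the plan says.** SAP Section 5.2.1.1 puts two conditions on FAS1. The subject in Group 1 or 2 must have received the study vaccine, and must "have a valid serology result for at least 1 serogroup from a BL provided 30 (window, +14) days post-vaccination".

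Section 5.2.1.2.1 makes PPAS1 a subset of FAS1 and lists nine deviations that remove a subject from it. The fifth is "Subject did not provide a post-dose serology sample in the pre-specified time window at 30 (window, + 14) days post-vaccination". The eighth is "Subject's post-vaccination serology sample did not produce a valid test result for any antigen".

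Section 5.2.3.1 runs the primary immunogenicity analysis on PPAS1 and states that it "will be confirmed on the Stage I Day 30 FAS (FAS1"). It names no other supporting set for that analysis. Section 5.3.2 rules out imputation of immunogenicity data.

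The pattern recurs twice. FAS2 requires subjects to "have a valid serology result for at least 1 serogroup from a BL provided 6 (window, 5–7) days post-vaccination", and PPAS2 (Section 5.2.1.2.2) excludes for the same window. FAS4 (Section 5.2.2.1) repeats the FAS1 wording for Groups 3 and 4, and PPAS3 (Section 5.2.2.2) repeats the PPAS1 exclusions.

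**The concern.** A full analysis set used to confirm a per-protocol result is useful to the extent that it puts back the subjects the per-protocol set left out. Here one such class can never be put back. A vaccinated subject with a valid titer drawn on Day 28 or Day 46 fails the FAS1 definition as written, so is in neither FAS1 nor PPAS1 and enters no Day 30 seroresponse analysis.

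If off-window subjects respond differently from the others, PPAS1 and FAS1 share the same selection on this point. Agreement between them then says nothing about it. This matters most for FAS1 in Group 1, because it stands behind the primary hypothesis test.

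**Working it through.** **Step 1. Set comparison.** A subject is removed by a PPAS1 exclusion only if that subject was in FAS1 to begin with.

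| PPAS1 exclusion (Section 5.2.1.2.1) | Already a condition of FAS1? | Can it act? |
|---|---|---|
| Sample outside the 30 (+14) day window | Yes | No |
| No valid result for any antigen | Yes | No |
| The other seven: eligibility, randomisation, vaccine preparation or administration, vaccination timing, prohibited therapy, unacceptable vaccine, other deviations | No | Yes |

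Two of nine exclusions are inert and 9 − 2 = 7 still operate. Of the two, only the window matters. A subject with no valid result for any antigen has nothing to analyse in any FAS when data are not imputed, so that item is harmless redundancy.

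The same comparison holds for PPAS2 within FAS2 and for PPAS3 within FAS4.

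**Step 2. Success rule.** Inputs: a serogroup succeeds if the one-sided 97.5% Clopper-Pearson lower limit exceeds 0.40 (Section 5.1.1.1); planned Group 1 size is 180 (Section 5.5). With x responders of n, the lower limit is the 0.025 quantile of Beta(x, n − x + 1).

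- 86/180: Beta(86, 95), 0.4029, pass
- 85/180: Beta(85, 96), 0.3975, fail

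So 86 responders are needed at n = 180.

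**Step 3. Effect at the boundary.** Assume 180 vaccinated subjects with a valid result for the serogroup, 85 responders, no other deviations, and two off-window subjects who are both non-responders.

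- As written, FAS1 = PPAS1 = 85/178: Beta(85, 94), 0.4023, pass on both
- FAS with off-window samples kept, 85/180: 0.3975, fail

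**Step 4. Larger assumed off-window counts.** The SAP gives no off-window rate. The rates below are assumptions, with 180 vaccinated and about 50% response among in-window subjects.

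| Off-window | As written, FAS1 = PPAS1 | Window-free FAS, no off-window responders | About 25% respond | 50% respond |
|---|---|---|---|---|
| 5% (9) | 86/171, 0.426, pass | 0.403, pass | 0.414, pass | 0.425, pass |
| 10% (18) | 81/162, 0.421, pass | 0.376, fail | 0.398, fail | 0.425, pass |

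At 5% the conclusion holds in this example even if no off-window subject responds. At 10% it changes only if off-window subjects respond much less often than the rest.

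**Step 5. How narrow the exposed range is.** With 9 off-window subjects, all non-responders, the decision differs when the total number of responders is 82 to 85. The as-written set passes from 82/171 (0.4027) and fails at 81/171 (0.3970); the window-free set needs 86/180. With two off-window non-responders, only a count of exactly 85 is affected.

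**The case against.** The expression for 30 days with its window is used throughout the SAP as the name of the visit. If it is only a label in Section 5.2.1.1, the PPAS1 window exclusion does act and there is no problem. This reading is weak, because Section 5.2.1.2.1 uses the same expression for what it calls the pre-specified time window. If a label was meant, the text still needs to say so, since two programmers could treat a Day 46 sample differently.

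The restriction can also be defended on substance. The primary endpoint in Section 4.1.1.1 is itself defined at 30 (+14) days, and the Day 6 objective concerns Days 5 to 7. A FAS open to samples of any date would blur what is measured. That has force against an unbounded FAS, and it is why the fix ties the sample to its assigned visit. It does not give the listed window exclusion any effect.

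The boundary example is a narrow one. The SAP states at least 90.0% power at n = 120; under the exact rule that implies a true rate of about 55.4%. At that rate the chance of exactly 85 responders of 180 is about 0.5%. The notes to Tables 3.2 to 3.4 also steer blood draws into the window, and nothing in the SAP suggests that off-window subjects respond differently. This stands and limits the size of the point.

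A reader might infer that FAS1 and PPAS1 must agree by construction. They need not: seven exclusions still separate them. A reader might also infer from the inert exclusions that a wider FAS was intended. The text does not support that either, because the no-valid-result exclusion stays inert under any FAS that requires a valid result. The list fits a standard deviation checklist equally well.

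**Conclusion.** The point holds for the sampling window. Read literally, the PPAS1 window exclusion cannot remove anyone, and the FAS1 analysis cannot show whether dropping off-window samples affects the primary conclusion. The no-valid-result exclusion is not a second defect.

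The consequence is greatest for FAS1, which supports a hypothesis test in Group 1 and, for Secondary Objective 1, in Group 2. It would be too strong to say that all three sets are meant to confirm a tested result. FAS2 is reported beside PPAS2 with no hypothesis, and FAS4 confirms a descriptive Stage II analysis.

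The effect is small unless a serogroup falls near the 40% bar. It rests on an assumed off-window count and an assumed lower response among those subjects; the SAP supplies neither. This is a gap in the stated robustness check, not evidence that the primary result would be wrong.

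**What to change.** In Section 5.2.1.1, define FAS1 as Group 1 and 2 subjects who received the study vaccine and have a valid result for at least one serogroup from the post-vaccination sample assigned to the Day 30 visit, whether or not it was drawn in the window. For consistency, reword FAS2 (Day 6 visit) and FAS4 (Stage II Day 30 visit) in the same way. Keep the window only as a PPAS exclusion. The no-valid-result item can stay or be deleted.

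The cost is three sentences in the SAP. PPAS results do not change. Sample timing in the FAS analyses becomes slightly less uniform.
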